Longitudinal evaluation of continuously measured secondary endpoints (e.g., EQ-5D-3L and FLS) may be performed using a linear regression model to evaluate the long term experience (e.g. change over time) of patients regarding these measures while on Plegridy. Categorical outcomes on healthcare resource consumption, treatment adherence, [REDACTED] and Plegridy prescription and utilization patterns will be summarized using frequencies and percentages. If necessary, a 95% CI based on binomial distribution might be provided for some of the categorical variables like patient adherence.

FLS-VAS includes the patients' ratings of effectiveness and satisfaction of controlling FLS with prophylactic regimens. The ratings will be summarized by mean (SD) and median (maximum and minimum). Changes of FLS-VAS ratings over time will also be summarized by mean (SD) and median (maximum and minimum). The changes of FLS-VAS ratings over time will be tested using a Wilcoxon rank-sum test. Longitudinal evaluation of FLS-VAS ratings using a linear regression model may be performed to evaluate patients' long-term experience (e.g., change over time) with the effectiveness and satisfaction of prophylactic regimens to control FLS while receiving Plegridy.

[REDACTED]

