
Study Size:
	
In Version 3.0 of this protocol, approximately 1600 patients across approximately 160 participating sites in the United States (US), European Union (EU), Australia, and sites participating in Study 105MS302 and 105MS303 in other countries were planned to be enrolled. In January 2017, following a decision by Biogen to limit enrollment to approximately 1100 patients, a Protocol Clarification Letter was sent to all study sites providing official notification that enrollment into the study should be stopped. The current target sample size is expected to provide acceptable precision around the estimates of the proportion of patients experiencing SAEs and ensure a reasonable likelihood of observing rare AEs over a 5-year period. The target sample size will also provide acceptable precision around the overall effectiveness endpoint of the proportion of patients with no evidence of disease activity clinically (cNEDA), which is defined as having no relapses and no disability progression.

Data Analysis:
	
Statistical analyses will be based on all patients who enroll in the study and receive at least one within-study dose of Plegridy. Analyses will be conducted separately for patients newly-prescribed Plegridy (Plegridy-naïve) from those who have previous exposure to Plegridy prior to study enrollment (Plegridy-experienced). Statistical analyses will generally be descriptive and exploratory in nature. No formal statistical hypothesis testing is planned.
 
Ninety-five percent confidence intervals (95% CIs) for the incidence and incidence rate point estimates will be calculated using the negative binomial distribution and the Poisson distribution, respectively. Analyses of continuous endpoints may include summaries of values over time, change from baseline over time, shift tables, and/or summaries of worst post-baseline values.
 
The proportion of patients with cNEDA will be calculated over time (e.g., Baseline to Year 1, Baseline to Year 2, etc.) as well as

CONFIDENTIAL

The information contained herein may not be used, disclosed, or published without the written consent of Biogen MA Inc.

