8.2.4.7. Long-Term Follow-Up

After enrollment, the Prescribing Physician will collect patient information during routine clinical visits as described in [Section 8.3](#). For the purposes of this study, routine clinical visits are defined as any visit scheduled per local standard of care. The collected information for each patient will be sent to the CRO managing the study (IQVIA, see [Section 8.5](#)) through the EDC system at baseline, approximately every three months (\pm four weeks) for the first year of follow-up and approximately every six months (\pm four weeks) for Year 2 through Year 5 of follow-up after enrollment. If the CRO does not receive completed data from the physician on a patient for whom follow-up is expected, the CRO will contact the site to remind them to complete the required data.

CONFIDENTIAL

The information contained herein may not be used, disclosed, or published without the written consent of Biogen MA Inc.

PROs may be completed by patients either electronically or on paper. PROs can be accessed electronically via a secure, personalized link either at the time of a routine clinic visit or outside of the clinic within four weeks of the routine visit. Alternatively, the PROs can be completed on paper at the time of a routine clinic visit. PROs will be collected at baseline (enrollment), approximately every three months for the first year of follow-up, and approximately every six months for Year 2 through Year 5 of follow-up after enrollment. If a patient does not complete the PROs during a routine clinic visit, the patient will be asked to complete the PROs within four weeks of each routine visit, if consistent with local regulations.

All information will be sent to the CRO electronically. The information received by the CRO will be stored in a secure database.

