8.3.7. Patient-Reported and Health Economics Outcomes

Patient assessment of the following outcome measures will be collected, if consistent with local regulations:

- Impression of functional health and well-being using the EQ-5D-3L index score and the five individual component scores. Refer to Section 16.2, Appendix 1.
- FLS Assessment: Patients will assign a score from “0” to “3” to their muscle aches, chills, fatigue, and body temperature as follows: “0” for absent; “1” for mild, did not interfere with daily activities; “2” for moderate, sufficient to interfere with daily activities; and “3” for severe, bed rest required. Refer to Section 16.3, Appendix 2.

FLS-VAS: This patient-reported assessment includes two VAS ratings and will be performed to evaluate any prophylactic regimen such as acetaminophen, ibuprofen, aspirin, or naproxen used to alleviate FLS. The first VAS will assess the effectiveness of the prophylactic regimen used by the patient to control FLS. Patients will rate their prophylactic regimen to control FLS between “not effective” to “very effective”. The second VAS will evaluate the patient’s satisfaction with the effectiveness of the prescribed regimen to control FLS. Patients will rate their satisfaction from “not satisfied” to “very satisfied.” Refer to Section 16.7, Appendix 6.

Note: If a patient selects “Absent” for Question 1 of the FLS Assessment, then the FLS-VAS does not need to be completed for that patient.

- Healthcare resource consumption questionnaire: This patient-reported questionnaire will ask patients to report the frequency of MS-related, non-MS-related, relapse-related hospitalizations, MS-related neurological visits, MS-related ER visits, and visits to other health care professionals for MS-related and other reasons. Refer to Section 16.4, Appendix 3.
- Treatment adherence questionnaire: This is a patient-reported questionnaire that measures adherence to Plegridy treatment in the past 28 days, the number of missed injections, and reasons for discontinuation, if applicable. Refer to Section 16.5 and Section 16.6, Appendices 4 and 5.

Refer to Section 16.1 for the timing of assessments.

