8.6.3. Demography and Baseline Disease Characteristics

Demographic and baseline disease characteristics will be summarized overall. The demographic profile (age, sex, and race [where legally allowed]), relevant medical history, MS disease history, MS treatment prior to start of Plegridy, and concomitant medications and therapies used will be listed and summarized using appropriate descriptive statistics for categorical and continuous variables. Categorical variables will be summarized using frequencies and percentages. Continuous variables will be summarized using mean, SD, median, and maximum and minimum values. Two-sided

CONFIDENTIAL

The information contained herein may not be used, disclosed, or published without the written consent of Biogen MA Inc.

95% CIs will be used. In general, categorical data will be summarized using frequency and percentage, and continuous variables will be summarized using descriptive statistics (number, mean, SD, median, minimum, and maximum). For continuous variables, if the data are approximately normally distributed, then a 95% CI for the mean change will be calculated. If the data are not normally distributed, then the interquartile range will be presented with the median. All analyses will be conducted using a two-sided test and a significance level of 0.05. Due to the inherent differences in Plegridy-naïve patients and those who had exposure to Plegridy prior to study enrollment, analyses will be conducted separately for these two groups. The definition of Plegridy-naïve will be described in the SAP.

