8.6.5.4. Secondary Endpoints Analysis

Plegridy prescription and utilization

Duration of Plegridy use and prescribed dosing frequency will be summarized both descriptively and categorically, as appropriate. Primary reasons for discontinuation of Plegridy will be tabulated. Plegridy use will also be described by concomitant medications.

Clinical disease activity (relapse activity and disability progression)

Relapse activity will be assessed by evaluating by relapse-related endpoints. These analyses will include the following parameters:

- ARR: defined as the total number of relapses divided by the number of patient-years on study divided by 12 months.
- Time to first relapse: defined as time (in days) between the date of initiating Plegridy to date of onset of first relapse following Plegridy initiation. Please refer to Section 8.3.6 for the definition of relapse.

CONFIDENTIAL

The information contained herein may not be used, disclosed, or published without the written consent of Biogen MA Inc.

- Proportion of patients with relapse: The proportion of patients with relapse will be described by counts and percent.
- Distribution of the number of relapses: The distribution of the number of relapses will be summarized using mean (SD) and median (minimum and maximum).

Disability progression will be assessed by evaluating disability progression-related endpoints. These analyses will include the following parameters:

- Proportion of patients with sustained progression for at least six months. For the purposes of this study, progression is defined as at least a 1.0 point increase from baseline in EDSS ≥ 1.0 or at least a 1.5 point increase from a baseline EDSS = 0.
- Time to sustained progression for at least six months.

ARR will be analyzed using a negative binomial model, adjusted for appropriate prognostic factors. If the data are under-dispersed or if the negative binomial regression model does not converge, a Poisson regression model with the same covariates will be used instead. Time to sustained progression will be analyzed using Kaplan-Meier estimates.

In addition, Poisson regression model and Cox proportional hazard model might be applied to assess the association between certain demographic variables, baseline disease characteristics, or medical history variables of interest and ARR/time to sustained disability progression, respectively.

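### Change in FLS-VAS ratings within the same patients is tested with the Wilcoxon rank-sum test, a test for two independent groups

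*Protocol*

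**What the plan says.** Change in the FLS-VAS over time is part of a secondary objective (Protocol Section 7.3) and is a listed secondary endpoint (Section 8.1.2). Section 8.6.5.4 fixes the test: "The changes of FLS-VAS ratings over time will be tested using a Wilcoxon rank-sum test". The same section also summarises these changes by mean, SD, median and range.

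The ratings are repeated on each patient. Section 8.2.4.7: "PROs will be collected at baseline (enrollment), approximately every three months for the first year of follow-up", then about every six months in Years 2 to 5. Not every patient rates at every visit. Section 8.3.7: "If a patient selects “Absent” for Question 1 of the FLS Assessment, then the FLS-VAS does not need to be completed for that patient".

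On grouping, Section 8.6.3 says of patients new to Plegridy and those with "exposure to Plegridy prior to study enrollment, analyses will be conducted separately for these two groups".

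On testing in general, the Abstract says "No formal statistical hypothesis testing is planned", while Section 8.6.3 says "All analyses will be conducted using a two-sided test and a significance level of 0.05".

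**The concern.** The rank-sum test takes the two sets of ratings as coming from different people. Change over time compares each patient with himself or herself. If patients who rate high at one visit tend to rate high at the next, the test overstates the variability of the difference, so its p-values are too large.

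At stake is whether a real change in how well prophylaxis controls flu-like symptoms is detected. The wording is a commitment to one named test, so a SAP that follows the protocol carries the error forward. Section 8.6.6 plans interim analyses annually after the first, with results going to congress abstracts, so the wrong p-value could be published more than once.

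The protocol also leaves unclear whether this p-value is wanted at all.

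**Working it through.** **Inputs from the protocol.** Rank-sum test (Section 8.6.5.4); two-sided 0.05 (Section 8.6.3); scheduled ratings at months 0, 3, 6, 9 and 12, then every 6 months from 18 to 60, which is 5 + 8 = 13 per patient at most (Section 8.2.4.7). No stated figure rests on this test, so there is none to reproduce.

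**Assumptions, because the protocol gives no values.** Within-patient correlation ρ of 0.3, 0.5 and 0.7; a shift d of 0.15 SD; 100, 200 or 400 patients rated at both of two times.

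**Step 1: is there a two-group reading?** The only two groups defined for the analyses are Plegridy-naïve and Plegridy-experienced patients, and Section 8.6.3 analyses them separately. Section 8.6.5.4 names no other groups for the FLS-VAS. The comparison is therefore between times, within patients.

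**Step 2: true size.** With n patients rated twice (SD 1), the rank-sum test behaves as if the variance of the difference were 2/n. It is actually 2(1 − ρ)/n. The test statistic then has SD √(1 − ρ) instead of 1, and the size is 2Φ(−1.96/√(1 − ρ)).

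| ρ | 1.96/√(1 − ρ) | Rank-sum size, formula | Rank-sum size, simulated |
|---|---|---|---|
| 0.3 | 2.343 | 1.9% | 1.5–2.2% |
| 0.5 | 2.772 | 0.6% | 0.7–0.8% |
| 0.7 | 3.578 | 0.03% | 0–0.15% |

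The simulations used rounded 0–10 ratings, 100 and 400 pairs, 2000 runs each. The signed-rank test held 4.0–5.6% in the same runs.

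**Step 3: power.** For normal data the rank-sum statistic has mean λ = d·√(n/2)·√(3/π). With n = 200, λ = 0.15 × 10 × 0.977 = 1.466.

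- Rank-sum: Φ((λ − 1.96)/√(1 − ρ)) gives 28%, 24% and 18% at ρ = 0.3, 0.5 and 0.7.
- Signed-rank: Φ(λ/√(1 − ρ) − 1.96) gives 42%, 55% and 76%.

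Simulation agrees closely (rank-sum against signed-rank):

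| Pairs | ρ = 0.3 | ρ = 0.5 | ρ = 0.7 |
|---|---|---|---|
| 100 | 14% v 22% | 9% v 29% | 5% v 43% |
| 200 | 29% v 43% | 25% v 53% | 19% v 75% |
| 400 | 55% v 68% | 55% v 81% | 56% v 96% |

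At 880 pairs, an upper bound from 1100 patients less the 20% dropout in Section 8.6.7, λ = 0.15 × √440 × 0.977 = 3.075. The formulas give 91% v 96% at ρ = 0.3 and 94% v 99% at ρ = 0.5.

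**Step 4: incomplete pairs.** If only a fraction f of the ratings at each time come from patients rated at both, the variance factor is 1 − fρ. With f = 0.5 and ρ = 0.5, 1.96/√0.75 = 2.263, and the size is 2.4%. Partial overlap softens the error but does not remove it.

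**Step 5: the statements on testing.** The Abstract and Section 8.6.7 describe a study without formal hypothesis tests. Section 8.6.3 puts every analysis under a two-sided 0.05 test, Section 8.6.5.4 names one, and item 2.1.4 of the Annex 2 checklist is ticked as stating hypotheses to be tested, with Section 8.6.5.4 among its references. These passages do not tell the reader whether the FLS-VAS p-value is meant to carry weight.

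**The case against.** **The error is conservative, and its size depends on assumptions.** This stands. No false positives arise under positive correlation. With several hundred pairs or a correlation near 0.3 the power loss is modest. The changes are also summarised descriptively, so reporting does not depend on the test.

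**The signed-rank test has its own difficulty.** This stands too. It uses only patients with both ratings, and because the scale is skipped when symptoms are absent, those patients are a selected group. The fix must say so.

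**One nominal test need not contradict the Abstract, which calls the analyses descriptive in general and rules out only formal testing.** This stands in part. The single test could pass as loose wording, but the sentence in Section 8.6.3 covers all analyses and does need reconciling.

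**A stronger reading that the protocol does not support.** A reader might infer that repeated patient-reported outcomes and relapse counts are also fitted with models that assume independence, giving wrong intervals throughout.

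- The longitudinal regression is optional ("may be performed using a linear regression model to evaluate the long term experience (e.g. change over time) of patients"), and the protocol states neither independence nor a correlation structure. That detail may be in the SAP. If ordinary least squares were run, the direction of error would vary. For a time slope with 13 visits, simulated null rejection was 0–1.3% under constant correlation and 4.5–7.5% with random slopes. The 39–54% found for a between-patient covariate concerns a term that this section does not describe.
- The planned relapse-rate model is negative binomial, which allows for over-dispersion. Poisson replaces it only for under-dispersed data or non-convergence. The separate association model is again optional ("Poisson regression model and Cox proportional hazard model might be applied to assess the association"), and its variance method is left open. Poisson standard errors of 0.81 to 0.57 of the true value follow only if the dispersion is 0.5 to 2 and the relapse rate is 0.3 per year over 3.4 years, all assumed.

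**Conclusion.** The rank-sum test is the wrong test for the comparison that Section 8.6.5.4 describes, and this can be read from the protocol without the SAP. The test's independence assumption fails, its true size falls well below 5%, and it loses power. Over assumed correlations of 0.3 to 0.7 the large-sample size runs from about 2% to under 0.1%. At 200 pairs and a 0.15 SD shift, power falls short of the signed-rank test by about 14, 28 and 56 percentage points (43 − 29, 53 − 25, 75 − 19). The figures depend on the assumed correlation, shift and number of complete pairs; the direction needs only positive correlation.

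The consequence is limited to missed change in one secondary patient-reported endpoint. Neither primary endpoint, SAE incidence or cNEDA, is touched. The conflict over whether tests are planned is a matter of wording to settle. The optional regression and Poisson models are points to align, not demonstrated errors. The sentence should be corrected, but the point is not serious enough to put the study's main conclusions in doubt.

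**What to change.** 1. In Section 8.6.5.4, replace the rank-sum test with the Wilcoxon signed-rank test on within-patient change between stated times. Alternatively, report the median within-patient change with a 95% CI and no p-value, which fits the Abstract better.
2. At each time, report the number of patients with both ratings, and state that they are a selected subset because the scale is skipped when symptoms are absent.
3. Reconcile the sentence on two-sided tests in Section 8.6.3 with the Abstract and Section 8.6.7, for example by limiting it to any nominal p-values that are kept and labelling those exploratory.
4. Minor alignments: if the longitudinal regression is run, fit it as a mixed model for repeated measures, which also uses patients without complete pairs. If the relapse-association model is run, use the negative binomial model already chosen for the relapse rate, or Poisson with robust variance.

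The cost is a few lines in the protocol or SAP and a different SAS procedure. No new data are needed.

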8.6.6. Interim Analyses

At a minimum, interim analyses are planned after at least 250 patients have completed one year of follow-up and annually thereafter.

Data from interim analyses will be submitted, at minimum, as abstracts to relevant congresses.

8.6.7. Sample Size Considerations

While no formal statistical hypotheses are being tested in this descriptive observational study, 1100 patients newly or currently prescribed with Plegridy are being targeted for enrollment. All patients will be followed for up to five years, and follow-up is planned regardless of whether patients discontinue treatment with Plegridy. Because this is a long-term observational program, a sample size of 1100 patients was chosen to ensure a reasonable likelihood of observing rare AE events over a 5-year period and to provide informative CIs for SAE incidence and incidence rate point estimates. Based on the withdrawal/discontinuation rates observed in the Plegridy Phase III clinical trial (Study

CONFIDENTIAL

The information contained herein may not be used, disclosed, or published without the written consent of Biogen MA Inc.

105MS301, 1-year) and prior Biogen observational studies, it is expected that approximately 3520–3960 person-years of follow-up will accrue.

With a sample size of 1100 patients, the probability of observing an event with an incidence rate of 0.10% (1/1000 persons) will be approximately 67%; the probability of observing an event with an incidence rate of 0.09% (90/100,000 persons, or 1/1111 persons) will be approximately 63%; the probability of observing an event with an incidence rate of 0.08% (80/100,000 persons, or 1/1250 persons) will be approximately 59%; and the probability of observing an event with an incidence rate of 0.054% (54/100,000 persons, or 1/1851 persons) will be approximately 48%.

For the co-primary endpoint of cNEDA, assuming a dropout rate up to 20%, a sample size of 1100 patients, and an expected 68.4% of patients free from clinical disease activity at the end of one year (Study 105MS301, 1-year), a two-sided 95% CI for the observed proportion of patients free from measured clinical disease activity at the end of one year using large sample normal approximation will extend 0.027 to 0.031 from the observed proportion for an expected proportion of 0.684.

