8.6.4. Safety

8.6.4.1. Analysis Population

Statistical analyses will be based on all patients who enroll in the study (defined as having an available date of informed consent) and receive at least one within-study dose of Plegridy. Safety analyses will be conducted separately between Plegridy-naïve patients and those who had exposure to Plegridy prior to study enrollment. The definitions will be further described in the SAP.

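### Section 8.6.7: the detection probability at 0.054% is about 45%, not 48%, and the cNEDA half-width of 0.027 to 0.031 holds only for a pooled estimate

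*Protocol*

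**What the plan says.** Section 8.6.7 supports the sample size with two sets of figures.

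- **Detection of rare events.** It begins "With a sample size of 1100 patients, the probability of observing an event with an incidence rate of 0.10% (1/1000 persons) will be approximately 67" per cent, continues with "an incidence rate of 0.09% (90/100,000 persons, or 1/1111 persons) will be approximately 63" per cent, gives 59% for an incidence of 0.08%, and ends with "the probability of observing an event with an incidence rate of 0.054% (54/100,000 persons, or 1/1851 persons) will be approximately 48" per cent.
- **Precision for cNEDA.** With an expected proportion of 0.684 at one year, 1100 patients and up to 20% dropout, the 95% interval "will extend 0.027 to 0.031 from the observed proportion".

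Both sets rest on a single cohort, since "1100 patients newly or currently prescribed with Plegridy are being targeted for enrollment". On how the data will be analysed, Section 8.6.3 says that "analyses will be conducted separately for these two groups", meaning Plegridy-naïve patients and those exposed before enrolment. The data analysis entry of the abstract says the same of analyses in general. Section 8.6.4.1 repeats it for safety: "Safety analyses will be conducted separately between" the two groups. Section 8.6.4.2 defines incidence as a proportion of patients, and incidence rate as a measure adjusted for duration of follow-up.

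**The concern.** Two things do not fit. First, the last of the four probabilities looks too high beside the other three. From 0.08% to 0.054% the expected number of events falls from 0.88 to 0.594, yet the stated probability falls only from 59% to 48%. This is the rarest event listed, in a section meant to show that the study has a fair chance of seeing rare events, and the error flatters the design.

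Second, the only interval width given for a co-primary endpoint describes a cohort that the general analysis statements say will be divided. If cNEDA is reported by prior exposure, each interval will be wider than the protocol leads its reader to expect. The study-size entry of the abstract relies on this figure when it calls the precision for cNEDA acceptable.

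**Working it through.** **Detection probabilities**

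Inputs from Section 8.6.7: n = 1100; p = 0.10%, 0.09%, 0.08% and 0.054%.

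Formula: P(at least one event) = 1 − (1 − p)^n.

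| p | Stated | Computed, n = 1100 |
|---|---|---|
| 0.10% | 67% | 66.7% |
| 0.09% | 63% | 62.9% |
| 0.08% | 59% | 58.5% |
| 0.054% | 48% | 44.8% |

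The first three reproduce and the fourth does not. Reasonable variants do not rescue it:

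- The Poisson form, 1 − exp(−1100 × 0.00054) = 1 − exp(−0.594), gives 44.8%.
- p = 1/1851 gives 44.8%.
- Letting p run over its rounding range, 0.0535% to 0.0545%, gives 44.5% to 45.1%.
- n = 880 or 990 (20% or 10% dropout) gives 37.8% or 41.4%.
- n = 1600 or 3000 (the superseded sample sizes) gives 57.9% or 80.2%.
- n = 3520 or 3960 (the forecast person-years) gives 85.1% or 88.2%.

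To reach 48% would take p of about 0.059% (p = 0.06% gives 48.3%) or n of about 1211. The text states the incidence in three forms that agree with one another (a percentage, a count per 100,000 and one in 1851), so the probability is the figure that is out of line.

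**cNEDA half-width**

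Inputs from Section 8.6.7: proportion 0.684; n = 1100, or 1100 × 0.8 = 880 after dropout.

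Formula: 1.96 × √(0.684 × 0.316 / n).

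- n = 1100: 1.96 × √(0.216144 / 1100) = 0.0275
- n = 880: 1.96 × √(0.216144 / 880) = 0.0307

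This reproduces the stated 0.027 to 0.031, and shows that it uses the pooled cohort.

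The naïve/experienced split is not in the document, so the group sizes below are assumptions chosen to show the range.

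| Assumed group size | Half-width, no dropout | Half-width, 20% dropout |
|---|---|---|
| 990 (90%) | 0.029 | 0.032 |
| 770 (70%) | 0.033 | 0.037 |
| 550 (50%) | 0.039 | 0.043 |
| 330 (30%) | 0.050 | 0.056 |
| 110 (10%) | 0.087 | 0.097 |

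**Do separate analyses change the chance of seeing an event?**

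For groups of size n1 and n2 with the same p, the chance of no event in either is (1 − p)^n1 × (1 − p)^n2 = (1 − p)^(n1 + n2). With two groups of 550 and p = 0.10%, each group alone has probability 42.3%, and the study as a whole has 1 − (1 − 0.423)² = 66.7%. That is the pooled figure.

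**The case against.** The strongest reply is that little turns on this. The study is descriptive, tests no formal hypothesis, and closed enrolment in January 2017, before this version of the protocol. A slip of about three points in one of four approximate figures changes no estimate, endpoint or decision. That stands, and it sets the severity.

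It can also be said that a pooled cNEDA estimate is not ruled out. Section 8.6.5.2 foresees summaries of the whole study population as well as of subgroups, and Sections 8.6.5.1 and 8.6.5.3 mention no division by prior exposure. Section 8.6.4.1 does require the division, but only for safety. This stands in part. A reader might infer that no planned estimate can have the stated precision; the document does not go so far. What remains is an unresolved tension with the abstract and Section 8.6.3, which are general in scope.

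Two further readings are tempting and are not supported.

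- A reader might infer that all four detection probabilities are overstated because safety is analysed by group. Section 8.6.7 speaks of observing an event with 1100 patients and claims nothing per group. The last calculation above shows that separate tabulation leaves the study-wide probability unchanged.
- A reader might want the probabilities rebased on the forecast that 3520 to 3960 "person-years of follow-up will accrue", which is 64% to 72% of 1100 × 5 = 5500. With a constant hazard, an assumption that the protocol does not make, a 0.10% five-year risk would give 51% to 55%, and a 0.10% rate per person-year would give 97% to 98%. The correction has no settled direction. Each frequency is expressed per persons, so the per-patient reading is plain and only the label is loose. Nor is the forecast clearly the time at risk: Sections 8.2.4.4, 8.2.4.9 and 10.2.2 tie some collection after discontinuation to 30 days from the last dose.

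**Conclusion.** The 48% is wrong as written. At a per-patient incidence of 0.054% and 1100 patients the probability is 44.8%, an overstatement of 3.2 percentage points; the other three figures are right. This needs no assumption beyond the independence between patients that the protocol's own figures imply.

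The cNEDA half-width is computed correctly, but only for a pooled estimate that the protocol does not clearly declare and that its general statements on separate analysis appear to replace. Any division makes both groups less precise than stated. By how much depends on a split that the document does not give; an equal split would widen the interval by a factor of √2, to 0.039, or 0.043 after dropout.

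The pooled detection probabilities may stay as study-wide figures. Calling the underlying quantity an incidence rate conflicts with the protocol's own definitions and should be tidied. Overall the point is minor.

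**What to change.** In Section 8.6.7:

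1. Change 48% to 45%.
2. For the cNEDA half-width, do one of two things. Either say that it applies to a pooled estimate and declare that estimate in Section 8.6.5.3, beside the separate analyses; or give it for the naïve and experienced groups using the actual split, once the definition of Plegridy-naïve that Section 8.6.3 defers to the SAP has been applied.
3. Say that the four detection probabilities are study-wide, and call the frequencies incidence (proportion of patients), in line with Section 8.6.4.2. No rebasing on person-years is needed.

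The cost is a text change. No patients, data or analyses are added unless the sponsor chooses to declare a pooled cNEDA estimate. The stated figures become slightly less favourable.

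### The 48% chance of observing an event of incidence 0.054% does not follow from 1100 patients; the calculation behind the other three figures gives 45%

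*Protocol*

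**What the plan says.** Section 8.6.7 explains the target of 1100 patients partly by the prospect of seeing rare adverse events over five years, and partly by informative confidence intervals for serious adverse events. For the first reason it gives four probabilities in one sentence, all tied to the same 1100 patients:

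- "With a sample size of 1100 patients, the probability of observing an event with an incidence rate of 0.10% (1/1000 persons) will be approximately 67" percent
- "incidence rate of 0.09% (90/100,000 persons, or 1/1111 persons) will be approximately 63" percent
- "incidence rate of 0.08% (80/100,000 persons, or 1/1250 persons) will be approximately 59" percent
- "incidence rate of 0.054% (54/100,000 persons, or 1/1851 persons) will be approximately 48" percent

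No formula is printed. The same section expects "approximately 3520–3960 person-years of follow-up will accrue" and, for the clinical no-evidence-of-disease-activity (cNEDA) endpoint only, allows for dropout: "assuming a dropout rate up to 20%, a sample size of 1100 patients".

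**The concern.** The four figures belong to one series and should come from one calculation, with only the incidence changing. The first three do. The fourth is higher than that calculation allows.

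These are the only numbers the protocol gives for its claim about detecting rare events, and the incidence of serious adverse events is a primary objective (Section 7.2). The figure in error is the one for the rarest event listed, where detection is weakest, and it makes the study look slightly more sensitive than it is.

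**Working it through.** **Inputs**, all from Section 8.6.7: n = 1100; p = 0.0010, 0.0009, 0.0008 and 0.00054; stated probabilities 67%, 63%, 59% and 48%.

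**Formula.** The chance of at least one event among n patients, each with probability p, is 1 − (1 − p)^n. The Poisson form is 1 − exp(−np).

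**Step 1: the plan's figures at n = 1100.**

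| p | Stated | 1 − (1 − p)^1100 | 1 − exp(−1100p) |
|---|---|---|---|
| 0.0010 | 67% | 66.73% | 66.71% |
| 0.0009 | 63% | 62.86% | 62.84% |
| 0.0008 | 59% | 58.54% | 58.52% |
| 0.00054 | 48% | 44.80% | 44.79% |

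The first three match to the whole percent. The fourth is off by 48.0 − 44.8 = 3.2 points. Using 1/1851 for p gives 44.81%.

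**Step 2: rounding of p.** Any p that rounds to 0.054% (0.0535% to 0.0545%) gives 44.5% to 45.1%.

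**Step 3: what would give 48%.**

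- At n = 1100, p = 1 − 0.52^(1/1100) = 0.0594%, or about 1 in 1683. A result that rounds to 48% needs p of about 0.0586% to 0.0603%; p = 0.06% gives 48.3%.
- At p = 0.00054, n = ln(0.52)/ln(1 − 0.00054) = 1211, or about 1193 to 1229 allowing for rounding. The protocol names no sample size in that range.

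**Step 4: other readings at p = 0.00054.**

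| Reading | Probability |
|---|---|
| n = 880 (20% dropout) | 37.8% |
| 3520 person-years | 85.1% |
| 3960 person-years | 88.2% |
| Superseded target, n = 1600 | 57.9% |
| Superseded target, n = 3000 | 80.2% |
| At least two events, n = 1100 | 12.0% |

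None gives 48%.

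**Step 5: neighbouring figures.** The cNEDA half-widths in the same section do reproduce: 1.96 × √(0.684 × 0.316/1100) = 0.027, and 0.031 with n = 880. The slip is isolated.

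**The case against.** The strongest reply is about weight. Sections 3 and 8.1 say that 1100 followed a sponsor decision to limit enrollment, so these probabilities describe what that number offers more than they determined it. No target probability is set that 48% meets and 45% misses, and both are below even odds. Enrollment closed in January 2017, no formal hypothesis is tested, and the figure feeds no interval, endpoint or stopping rule. All of this stands and limits the importance of the point.

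Two further replies concern the arithmetic. First, the formula is inferred, not printed. That is true, but three figures in the same sentence fit it to the whole percent, so the inference is firm. Second, the figure is labelled approximate. The same label is attached to the other three, and each of those is within half a point of the computed value, so it does not cover a 3.2-point gap.

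**Conclusion.** The figure is wrong as written. With 1100 patients and an incidence of 0.054%, the probability of observing at least one event is 44.8%. The stated 48% overstates it by 3.2 points, and the chance of missing such an event is 55% instead of 52%. This assumes that the fourth figure was meant to be computed like the other three, with 1100 patients and a per-person probability.

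The protocol does not show which number slipped. The sample size is common to all four figures, and the incidence is written in three ways that agree, so the probability is the most likely error. The practical effect is modest: a correction to a stated detection property, with no change to design, conduct or analysis.

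**What to change.** In Section 8.6.7, change the last probability from 48% to 45%, and check the source calculation first. If that check shows that 48% was the intended figure, the incidence would have to be restated as about 0.06% (60/100,000, or 1/1667), which gives 48.3%. This is the less likely repair, because all three expressions of the rate would have to change together.

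Printing the formula beside the four figures would let a reader verify them. The cost is one number and, optionally, one line of text; the stated detection probability becomes slightly less favourable.
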